5.8 Extent of Exposure

The duration of total exposure to the investigational product in days will be determined from the first and last dosing dates during the treatment period and is derived as the last dose date – the first dose date + 1. The last dose date will be the date the last tablet was taken regardless of whether this is an active or inactive tablet. The total extent of exposure across all subjects in years will be derived by summing the total exposure in days across all subjects in the Safety Population and dividing it by 365.25 to convert the units

from days to years. This will be used in the derivation of event rates for adverse events as this represents the duration of the on-treatment period for treatment emergent adverse events.

The duration of actual exposure to the investigational product in days will be determined by subtracting the total number of days where no pills were taken from the duration of total exposure. The total number of days where no pills were taken is equivalent to the total number of missed pills from Section 5.7 summed across all cycles for that subject. Days where no pills were taken include days between Day 28 of a cycle and Day 1 of the next cycle where there are gaps between cycles and days within a cycle where there are no active or inactive pills taken. The total extent of actual exposure across all subjects in years will be derived by summing the exposure in days across all subjects in the Safety Population and dividing it by 365.25 to convert the units from days to years.

The duration of actual exposure will be used to determine whether or not a subject has had at least 26 weeks exposure and whether or not a subject has had at least 52 weeks exposure.

The number of cycles of treatment will be derived for each subject by determining the number of cycles as per the definition provided in Section 5.1.

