9.6.3.1 Adverse Events

AEs will be assessed from the time of signing the IC until exit from the study. At every study visit from Visit 2, subjects will be asked an indirect standard question to elicit any medically related changes in their well-being. They will also be asked if they have been hospitalized, had any accidents, used any new medications, or changed any current medication regimens (both prescription and over-the-counter medications).

Definition of Terms

Adverse Event (AE): Any untoward medical occurrence associated with the use of a drug in humans, whether or not considered drug related. In addition to novel events, an AE may be an exacerbation of a pre-existing medical condition that was present before the subject was assigned to a treatment group. Each AE is described using all three of the following classifications: expected or unexpected; related or unrelated; and serious or non-serious. Additionally, intensity of the event is also described.

Treatment-emergent adverse event (TEAE): A TEAE is any AE not present prior to the initiation of the treatments or any event already present that worsens in either intensity or frequency following exposure to the treatment. Since the starting point for AEs collection is the signing of the IC, not the start of the study treatment, the AEs recorded prior to first investigational product administration are designated as AEs while those that occur or worsen after the initiation of the investigational product are designated as TEAEs.

Exacerbation of Pre-Existing Medical Condition: An increase in the frequency or severity of a medical condition that is present before first investigational product administration. Any medical condition that is present before first investigational product administration and that does not deteriorate should not be reported as an AE.

Amendment Final Version 1.1

Expected: The determination of whether an AE is expected is based on previous experience with the investigational product, as follows:

Expected AEs are AEs that have already been identified during the investigational product's use, or are a known complication of standard medical procedures that may be conducted as part of the clinical study.

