5.3 On-Treatment Period

For contraceptive efficacy, the On-Treatment Period is defined as the period of time between the date of first dose of study medication and 7 days after the last dose of study medication (regardless of whether this is an active or inactive table), inclusive. If the subject has a pregnancy after the first dose of study medication and prior to the last dose of study medication, the On-Treatment Period is defined as the period of time between the date of first dose of study medication and the date of the estimated date of conception, inclusive. If the subject has a pregnancy when they are still on study medication but the estimated date of conception is missing because the date was not confirmed in an ultrasound, then the cycle and day of the estimated conception that is assigned from the narrative will be used to determine the end date.

For TEAEs, the On-Treatment Period is defined as on or after the date of first dose of study medication.

For medications, the On-Treatment Period is defined as the period of time between the date of first dose of study medication and the date of last dose of study medication (regardless of whether this is an active or inactive table), inclusive.

If the subject had a period of time when study medication was not being taken between the date of first dose of study medication and the last dose of study medication, this time will still be considered to be during the On-Treatment Period.

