5.11 Treatment-Emergent Adverse Event (TEAE)

A TEAE is defined as an AE with a start date or worsening during the On-Treatment Period for TEAEs (see Section 5.3 for definition of the On-Treatment Period).

If the start date for an AE is missing and the end date is either missing or on or after the date of first dose of study medication, then the AE will be assumed to be treatment-emergent. However, if the start date for an AE is missing and the end date is recorded and is before the first dose of study medication, then the AE will be assumed to be non-treatment emergent.

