5.15.5 Missing or Partial Treatment Start and Stop Dates

5.15.5.1 Missing Treatment Start and Stop Dates

If the subject has no diary data but has a pregnancy as per Principal Investigator's assessment in the pregnancy narrative that is classified as on-treatment or post treatment, then the subject will be classed as treated. The treatment start date and treatment stop date would be unknown in this situation.

In the case of post-treatment pregnancies, the cycle for censoring for the cumulative event rates for pregnancies cannot be determined and this will be missing. The subject will also consequently have no evaluable cycles for the Pearl Index. In the case of on-treatment pregnancies, the cycle of conception from the narrative will be used in the derivation of the cumulative event rates for pregnancies and in the derivation of the Pearl Index no other cycles would be included in the denominator for that subject.

When classifying concomitant, pre- and post medication and treatment emergent AEs and defining the Baseline assessments, the treatment start date will be assumed to be the first date in which the investigational product was dispensed and the treatment end date will be assumed to be the discontinuation or completion date for that subject. However, the start and stop dates for study medication will remain missing and the compliance and exposure will not be calculated. Similarly, the cycle of discontinuation of study medication cannot be determined and therefore this would remain missing for such subjects. The subject will have no evaluable cycles for the bleeding analysis.

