5.15.5.2 Partial Treatment Start Dates

If the subject has a partial start date Cycle 1, and consequently a partial start date for study medication, then the partial start date will be presented in the listing. If the date of last dose cannot be derived as a result of the partial start date, then this will be blank in the listings as the end date is unknown.

In the case of an on-treatment pregnancy, the cycle of conception will be estimated from the available data. If the subject does not have an on-treatment pregnancy, then for the cumulative event rates for pregnancy, the subject will be censored in the cycle where the last pill intake was reported per the diary data. Cycle 1 will be included in the denominator for the Pearl Index following the rules in Section 5.1.1 and will be included in the bleeding analysis following the rules in Section 5.1.2.

In this case, when classifying concomitant, pre- and post medication and treatment emergent AEs and defining the Baseline assessments, the treatment start date will be assumed to be the first date in which the investigational product was dispensed. If the treatment end date cannot be determined as a result of the partial start date, then the date of last dose will be derived for the day in the diary where the last pill is reported and by assuming that the start date is the latest possible day. For example, if the partial start date is January 2017 and the last day with a pill reported is Day 4 of Cycle 1, then the assumed start date would be 31 January 2017 and therefore Day 4 of Cycle 1 would be 3 February 2017 and this would be used as the date of last dose. The diary data for pill intake will be used to derive compliance and exposure per the rules in the SAP.

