9.0 Statistical Methods

All analyses will be conducted using SAS version 9.4 or higher.

No formal statistical analyses will be performed in this study.

The following conventions will be used when presenting summary statistics for study data:

- Continuous variables will be summarized using the following descriptive statistics: number of subjects (n), mean, standard deviation (SD), standard error of the mean (SEM), median, minimum (min), maximum (max), 25th percentile (lower quartile or Q1) and 75th percentile (upper quartile or Q3)
- Categorical and count variables will be summarized by the number of subjects (n) and the percent of subjects in each category. For AE tables, m may also be presented which represents the number of events. Percentages will be presented to 1 decimal place

- The number of subjects or observations will be presented as an integer
- Mean, median, lower quartile and upper quartile will be presented to 1 decimal place more than the raw value
- Min and max will be presented to the same number of decimal places as the raw value
- Standard deviation will be presented to 2 decimal places more than the raw value, up to a reasonable number of decimal places (i.e., rarely more than 3 decimal places unless the nature of the data suggests this)
- The denominator for percentage calculations will be the number of non-missing observations at that visit. Where this isn't appropriate, the number of subjects in the relevant population will be used

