9.6 Safety Analyses

9.6.1 Adverse Events

TEAEs will be classified into a standardized terminology using the MedDRA system organ classifications and preferred terms. Version 20.0 of MedDRA will be used as coding dictionary. The incidence of TEAEs will be summarized for the Safety Population.

A summary of TEAEs including the number of events reported, the annual rate and the number and percentage of subjects reporting the following will be presented:

- Any TEAE
- Any TEAE leading to death
- Any treatment-emergent SAE
- Any TEAE leading to premature discontinuation from the study
- Any SAE related to study medication

TEAEs are defined in Section 5.11. The annual rate will be derived as the number of events divided by the total exposure across all subjects in years.

A breakdown of the number and percentage of subjects reporting each TEAE with the corresponding number of events, categorized by body system and preferred term coded according to the MedDRA dictionary, will be presented. Note that subjects are only counted once within each body system or preferred term but subjects with multiple events of a specific type will be counted once for each occurrence in the number of events column.

A further tabulation of these data, categorized by relationship to study drug, will be presented. Subjects with multiple events within a particular body system or preferred term will be counted under the category of their most drug-related event within that body system or preferred term in column for the number of subjects. In the column for the number of events, multiple events of a specific type and relationship will be counted once for each occurrence. Relationship to study drug is categorized as not related (not related and unlikely on the CRF) and related (possible, probable and highly probable on the CRF). This will be repeated for TEAEs leading to premature discontinuation from the study.

TEAEs will also be presented by severity. For each system organ class and preferred term, subjects are included only once, at the maximum severity. In the column for the number of events, multiple events of a specific type and severity will be counted once for each occurrence.

All adverse events (including non-treatment-emergent events) recorded on the CRF will be listed. The following listings will be generated in the Screened Population:

- All AEs
- AEs leading to premature discontinuation from the study

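### The annual TEAE rate can count events up to study exit but divides by first-to-last-dose time only, which SAP 5.8 wrongly equates with the TEAE period

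*SAP*

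**What the plan says.** Four parts of the SAP and one of the protocol bear on this.

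- **Numerator period.** SAP 5.3: "For TEAEs, the On-Treatment Period is defined as on or after the date of first dose of study medication". No end is given. The same section ends the efficacy period 7 days after the last dose and the medication period at the last dose.
- **Numerator events.** SAP 5.11: "A TEAE is defined as an AE with a start date or worsening during the On-Treatment Period for TEAEs".
- **Denominator.** SAP 5.8 defines total exposure per woman as last dose date minus first dose date plus 1, sums it over the Safety Population and divides by 365.25. It assigns this total to adverse event rates, "as this represents the duration of the on-treatment period for treatment emergent adverse events".
- **Rate.** SAP 9.6.1: "The annual rate will be derived as the number of events divided by the total exposure across all subjects in years". The section does not limit the events to those starting by the last dose.
- **Collection window.** Protocol 9.6.3.1: "AEs will be assessed from the time of signing the IC until exit from the study". TEAEs are queried at Visit 7 (Protocol 9.5.3.5), which falls on Day 16 to 23 of Cycle 14. The Early Termination Visit is set 16 to 23 days after the last intake and repeats the Visit 7 procedures (Protocol 9.5.4).

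**The concern.** The reason given in SAP 5.8 is contradicted by SAP 5.3 and 5.11. First-to-last-dose time does not cover the TEAE period, because that period continues after the last dose and collection continues with it. A woman with an event ten days after her last tablet adds one to the numerator, while those ten days add nothing to the denominator.

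The SAP's amendment log records that Amendment 2 changed the TEAE definition to take in everything from first dose onward, and it lists no matching change to 5.8. That may be how the two came apart.

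A second route leads to the same fault. Under SAP 5.15.5.1, a treated woman with no diary data has her TEAEs classified from assumed dates, but her exposure is not calculated. She can add events and no person-time at all.

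At stake is the one adverse event measure in SAP 9.6.1 that allows for differing follow-up. That matters when 45% dropout is planned, and the mismatch is proportionally largest in women who stop early. A reader of 5.8 would take the rate as matched when it is not.

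**Working it through.** The documents give no annual rate or person-year total to reproduce. The check compares the two windows and sizes the gap from planning values.

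**Inputs**

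- Full treatment: 13 × 28 = 364 days (SAP 5.1).
- Dropout 45%, at a mean of 4 cycles: 4 × 28 = 112 days (Protocol 12.1, stated for ages 16 to 35; applied here to all women as an assumption).
- Women treated: 2,000 (Protocol 12.1).
- Time from last tablet to exit: 16 to 23 days. For completers, Cycle 14 Day 16 to 23 is study day 364 + 16 = 380 to 364 + 23 = 387.
- Every woman attends the exit visit in window (assumption).

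**Planned denominator**

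- Mean exposure = 0.55 × 364 + 0.45 × 112 = 250.6 days.
- Total = 2,000 × 250.6 / 365.25 = 1,372 woman-years.

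**Unmatched time**

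- 2,000 × 16 / 365.25 = 88 woman-years, to 2,000 × 23 / 365.25 = 126 woman-years.
- Person-time to exit is therefore 1,460 to 1,498 woman-years.

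**Planned rate against a rate using person-time to exit (same events)**

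- Excess = 16 / 250.6 to 23 / 250.6 = 6.4 to 9.2%.
- Equivalently, the matched rate is lower by 16 / 266.6 to 23 / 273.6 = 6.0 to 8.4%.

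**Planned rate against a rate cut at the last dose**

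Let r be post-dose incidence divided by on-dose incidence. The documents do not give r. The excess is r × 16 / 250.6 to r × 23 / 250.6.

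| r (assumed) | Excess |
|---|---|
| 0 | 0% |
| 0.5 | 3.2 to 4.6% |
| 1 | 6.4 to 9.2% |

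**Sensitivity of the excess over the rate to exit**

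| Assumption | Calculation | Excess |
|---|---|---|
| 30% dropout | mean 0.70 × 364 + 0.30 × 112 = 288.4 days | 5.5 to 8.0% |
| 60% dropout | mean 0.40 × 364 + 0.60 × 112 = 212.8 days | 7.5 to 10.8% |
| 45% dropout, no early terminator attends an exit visit | 0.55 × 16 / 250.6 to 0.55 × 23 / 250.6 | 3.5 to 5.0% |

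**Per woman**

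- Completer: 16 / 364 to 23 / 364 = 4.4 to 6.3% of exposure.
- Early terminator at 4 cycles: 16 / 112 to 23 / 112 = 14.3 to 20.5%.

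Twenty-three days is not a strict upper limit. Protocol 9.5.4 sets none for a woman who comes to a scheduled visit having been off tablets for 16 days or more.

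**The case against.** The strongest reply is that this is a wording fault in one sentence. The formula in SAP 9.6.1 is explicit and reproducible, the annual rate is a SAP addition that Protocol 12.5.1 does not list, there is no comparison arm, and SAP 9.0 says "No formal statistical analyses will be performed in this study". On this view it would be enough to correct the sentence and label the denominator.

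The second reply is that 6.4 to 9.2% is not a bias estimate. It compares the planned rate with another denominator, and a longer denominator always lowers a rate. The alternative has a mirror-image cost: person-time to exit includes days off drug. If nothing starts after stopping, it falls 6.0 to 8.4% below the on-drug rate; if incidence halves, it falls 3.0 to 4.2% below (258.6 / 266.6 and 262.1 / 273.6). The planned rate errs upward, which is the cautious direction for safety.

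Much of this stands. The reach is small, the excess over an on-drug rate may be zero, and a rate to exit is not an on-drug rate. The per-woman figures describe individuals, not the pooled statistic. What does not follow is that the choice is only one of preference. The SAP itself says the denominator is meant to represent the TEAE period. Given the TEAE definition, person-time to exit meets that aim and first-to-last-dose time does not. A reader who wants an on-drug rate needs the numerator cut at the last dose as well, which the SAP does not do.

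**Conclusion.** The concern holds. SAP 5.8 states an equality that SAP 5.3 and 5.11 contradict, and the annual TEAE rate can count events from planned off-drug days missing from its denominator.

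On planning values the rate exceeds one using person-time to exit by 6.4 to 9.2%, or 3.5 to 5.0% if no early terminator returns. Whether it also exceeds a true on-drug rate depends on post-dose incidence, which the documents do not give. All these sizes rest on assumed dropout and attendance, not on trial data.

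Event counts, subject percentages, the tables by system organ class, relationship and severity, and the Pearl Index are unaffected. The point should be corrected, but it does not threaten the study's conclusions.

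**What to change.** 1. In SAP 5.8 and 9.6.1, divide TEAE counts by person-time from first dose to study exit, or to last contact for women lost to follow-up. The end must be the date of leaving the study, not of stopping tablets.
2. Correct the sentence in 5.8 that equates the two periods. Keep first-to-last-dose time for the exposure summaries.
3. For women with no dose dates, use the dates that SAP 5.15.5.1 already uses to classify TEAEs: first dispensing as the start, and for the end, "the treatment end date will be assumed to be the discontinuation or completion date for that subject". For partial start dates, use the start that SAP 5.15.5.2 applies to TEAE classification: "the treatment start date will be assumed to be the first date in which the investigational product was dispensed". Do not use the latest-possible-day rule there, which serves only to derive the last dose date. Dispensing can precede the first tablet, so these few women may gain some person-time; a footnote covers this.
4. State whether serious events reported from pregnancy follow-up after exit (Protocol 9.6.2.2) are in the count. If so, footnote them, because person-time to exit does not cover them.
5. If a rate per treatment-year is also wanted, show it as a second, labelled rate limited to events from first to last dose.

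**Cost.** Wording in two sections and one further person-time sum. The dates should largely be held already, although the documents do not name a last-contact field, so its availability is an assumption. The main rate needs no filter on event dates. The optional second rate does, and Protocol 9.6.3.1 does not list a worsening date among the required items. The reported rate falls by 6.0 to 8.4% on the assumptions above, and its label should say that it includes time off drug.

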9.4.4.2 Dosing Instructions

Each time investigational product is dispensed to the subject, site personnel will instruct the subject as follows:

- Take one pink tablet every day for 24 consecutive days (Day 1 through Day 24), followed by one white placebo tablet every day for 4 consecutive days (Day 25 through Day 28).
- When the pack of tablets is empty, start the next pack on the next day after the last white tablet of the previous pack has been taken. When starting a new pack of tablets, take the first pink tablet of the pack. There should be no interruption between two blister packs.
- Take the investigational product at approximately the same time each day throughout the study. The time of day should be determined by the subject.
- Return all blister packs to site personnel at the following visit.

9.4.4.3 Instructions in case of missed tablet(s) or in conditions potentially reducing the contraceptive efficacy

If the subject has vomiting or diarrhea within 4 hours of tablet intake, she should take another tablet from the extra pack (spare blister) as a replacement.

If the subject inadvertently misses one or more of the tablets, the following instructions must be followed⁶:

- If one active pink tablet is late (< 24 hours since a tablet should have been taken) or if one active pink tablet has been missed (24 to < 48 hours since a tablet should have been taken):
 - Take the late or missed active pink tablet as soon as possible.
 - Continue taking the remaining active pink tablets at the usual time (even if it means taking two active pink tablets on the same day).
 - Use of condom is not required.
- If two or more consecutive active pink tablets have been missed (\geq 48 hours since a tablet should have been taken):
 - If between Day 1 & Day 17:
 - Take the most recent missed active pink tablet as soon as possible (any other missed tablets should be discarded).
 - Continue taking the remaining active pink tablets at the usual time (even if it means taking two tablets on the same day).
 - Use condom or avoid sexual intercourse until 7 days of uninterrupted active pink tablet intake.
 - Consider emergency contraception as per current practice if the woman had unprotected intercourse during the missed pill interval.
 - If between Day 18 & Day 24:
 - Omit the hormone-free interval by finishing the active pink tablets in the current pack and starting a new pack the next day.

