 - If unable to start a new pack immediately, use condoms or avoid sexual intercourse until 7 days of uninterrupted active pink tablet intake from the new pack.
 - If this occurs during the last cycle, the subject should contact the study staff to know what she has to do with the next contraception.

If the subject inadvertently misses any of the white placebo tablets:

- Skip the missed white placebo tablet(s) and the remaining tablets are taken at the regular time.
- Use of condoms is not required during this time.

Amendment Final Version 1.1

Anytime a subsequent cycle of the product/pack is started later than the day following administration of the last white tablet, the subject should use condoms until she has taken pink tablets daily for 7 consecutive days.

9.4.4.4 In case of short-term intake of drugs that may decrease the efficacy of the COC

Subject is allowed to take drugs potentially decreasing the efficacy of the COC for a maximal period of 10 consecutive days (for example, CYP 3A4 inducers). Subjects must be instructed to use condoms when these drugs are used and during 7 days of uninterrupted pink tablet intake after finishing the medication.

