12.5.2 Extent of Exposure

The duration of exposure in days will be summarized using descriptive statistics for the Safety/ITT population. Duration of exposure will be calculated as the difference between last tablet intake date and the first tablet intake date plus 1.

Additionally, these summaries will present the number and percentage of subjects exposed for at least 26 weeks and at least 52 weeks. The denominators for calculating the percentages will be based on the number of subjects in the Safety population.

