5.0 Definitions

5.1 Cycle

The expected duration of a cycle is 28 days. A 28-day cycle consists of 24 days of active tablet intake followed by 4 days of inactive tablet intake and subjects who complete the study are expected to have completed thirteen 28-day cycles.

All cycles will be determined using the start dates recorded in the diaries. The first day of a cycle is the start date recorded on the diary for that cycle and the last day of a cycle coincides with the day before the start date recorded on the diary for the next cycle. However, because the last cycle of use has no start date for a following cycle, the last day of the cycle will be assumed to be the date of last dose of study medication, whether this is an active or inactive tablet. The date of last dose of study medication in the last cycle will be derived from the data collected in the diary.

If the conception is confirmed to be during a specific cycle in the narrative and this cycle is not in the diary data, then the cycle will be included as cycle in the exposure for the derivation of the Pearl Index. If the cycle in which conception occurred is not known, cycle(s) up to the one in which the positive pregnancy test occurred will be included in the exposure for the derivation of the Pearl Index.

For the analysis of bleeding data, the cycle will be shifted by 3 days with the 3 days of the next cycle included in the previous cycle. For example, in the bleeding analysis Cycle 2 will be from Day 4 of Cycle 2 to Day 3 of Cycle 3 inclusive.

The start and stop times of a cycle will be determined before determining whether the cycle is evaluable for the Pearl Index or evaluable for the bleeding data. Data review meetings may be held to determine if cycles are at-risk cycles for the Pearl Index and if they are evaluable for the bleeding analysis prior to database lock (see Section 8.3) if the classification is not clear from the data collected and the rules in the SAP.

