In addition, the subject diary data will be used to identify when a pill has been missed. The number of missed pills will be derived for each cycle. In this situation, a pill is assumed to be missed if there is a day in the diary without an entry for the number of tablets or with 0 active and 0 inactive pills reported as taken. Any gaps between Day 28 of a cycle and Day 1 of the next cycle will be included as missed pills. For example, if the reported start date for Cycle 1 is 1 February and the reported start date for Cycle 2 is 3 March, then the derived end date of Cycle 1 will be 2 March and 1-2 March will be included as 2 missed pills. If there are overlapping cycles in terms of dates, then the days will be included under the latest cycle and missed pills will be reported accordingly. For example, if the subject takes pills up to Day 24 in Cycle 1, then starts Cycle 2 on the same date as Day 25 of Cycle 1, so Days 25 to Day 28 of Cycle 1 will not be included in Cycle1 and these will not be counted as missed pills for Cycle 1.

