9.3.1 Extent of Study Drug Exposure

The overall duration of total exposure and actual exposure will be summarized using descriptive statistics. In addition, the total extent of exposure and total extent of actual exposure across all subjects will be summarized in years.

Additionally, the number and percentage of subjects exposed for at least 26 weeks and at least 52 weeks based on actual exposure will be presented. The denominators for calculating the percentages will be based on the number of subjects.

The number of cycles as defined in Section 5.1 will also be summarized using descriptive statistics. The number and percentage of subjects who had at least 1, 2, 3, etc. cycles will be summarized.

Exposure data will be listed for all subjects in the Safety Population.

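### The SAP counts 52-week exposure in pill-days, so on the planned 364-day schedule one missed or blank diary day disqualifies a woman who completed 13 cycles, contrary to Protocol 12.5.2

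*SAP*

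**What the plan says.** SAP 5.8 defines two durations. Total exposure is the calendar span from first to last dose, inclusive. Actual exposure is obtained by "subtracting the total number of days where no pills were taken from the duration of total exposure". The same section uses actual exposure to decide whether a woman reached 26 weeks "and whether or not a subject has had at least 52 weeks exposure". SAP 9.3.1 repeats this for the table: the number and percentage of women "exposed for at least 26 weeks and at least 52 weeks based on actual exposure will be presented".

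SAP 5.7.1 sets what counts as a day without a pill: "a pill is assumed to be missed if there is a day in the diary without an entry for the number of tablets", or a day with zero tablets recorded. Days between the end of one pack and the start of the next also count as missed.

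Protocol 12.5.2 defines one duration only: "Duration of exposure will be calculated as the difference between last tablet intake date and the first tablet intake date plus 1". It reports the 26- and 52-week counts among those same summaries and deducts nothing for missed days. Protocol 9.6.3.2 gives the same formula.

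On length of treatment, SAP 5.1 states that "subjects who complete the study are expected to have completed thirteen 28-day cycles". The SAP amendment log (12.1) records that actual exposure was added. It gives no reason for moving the threshold counts to it.

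**The concern.** The 52-week threshold equals the whole planned course. A measure that subtracts single days therefore leaves no slack, and the row stops describing women treated for a year. On the normal schedule it describes women with no missed or blank day inside any pack.

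This catches women who followed the protocol's missed-tablet instructions (Protocol 9.4.4.3). After one missed active tablet, the woman takes it late and continues, "even if it means taking two active pink tablets on the same day". For placebo tablets the instruction is: "Skip the missed white placebo tablet(s) and the remaining tablets are taken at the regular time". Neither lengthens the pack, so each leaves one pill-free day inside an unchanged 364-day span.

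The rule also orders women oddly. Two days without tablets between packs lengthen the span by two and are then subtracted, so that woman passes. One skipped inert tablet inside a pack fails.

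At stake is a reported safety-exposure count that could fall far below the number of completers, with no explanation in the tables and on a definition that differs from the protocol's.

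**Working it through.** **Planned length.** 13 cycles × 28 days = 364 days (SAP 5.1). This agrees with the end of the fourth reference period, Day 364 (SAP 5.1.2; 4 × 91 = 364). The threshold is 52 × 7 = 364 days. Slack at 52 weeks: 364 − 364 = 0. Slack for a completer at 26 weeks: 364 − 182 = 182 days.

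**Both definitions by intake pattern, for women who go through all 13 packs (threshold 364):**

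| Pattern | Total exposure (Protocol 12.5.2) | Actual exposure (SAP 5.8) |
|---|---|---|
| Perfect intake | 364, pass | 364, pass |
| One active tablet missed, doubled next day | 364, pass | 363, fail |
| One non-final placebo tablet skipped, or one blank diary day | 364, pass | 363, fail |
| One missed day in every cycle, none of them the last tablet | 364, pass | 351, fail |
| 2-day gap between packs | 366, pass | 366 − 2 = 364, pass |
| 1-day gap plus one missed day | 365, pass | 365 − 2 = 363, fail |
| Last tablet of Cycle 13 missed | 363, fail | 363, fail |
| One 4-day hormone-free interval omitted | 360, fail | 360, fail |

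The definitions part company on within-cycle missed or blank days before the last tablet. Gaps between packs cancel out, and the last two rows fail under both.

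**Possible size.** Planned dropout is about 45% (Protocol 12.1), so completers number 0.55 × 1800 = 990 at ages 16–35, or 0.55 × 2000 = 1100 if the same rate is applied to all ages. The daily chance *p* of a missed or blank day is not in the documents. I assume 0.1%, 0.5% and 1%, which is 0.4, 1.8 and 3.6 days per woman over 364 days.

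- (a) Same independent rate for every woman: pass fraction = (1 − p)^364.
- (b) Rates varying between women (assumed gamma, shape 0.5, mean 364p): pass fraction = (1 + 364p/0.5)^(−0.5).
- Total exposure: in this model only a missed final tablet matters, so pass fraction = 1 − p.

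| p | (a) fraction | (a) of 990 / 1100 | (b) fraction | (b) of 990 / 1100 | Total exposure, of 990 |
|---|---|---|---|---|---|
| 0.1% | 0.6948 | 688 / 764 | 0.7607 | 753 / 837 | 989 |
| 0.5% | 0.1613 | 160 / 177 | 0.4642 | 460 / 511 | 985 |
| 1% | 0.0258 | 26 / 28 | 0.3475 | 344 / 382 | 980 |

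Treating Day 1 as always taken (exponent 363) changes 688 to 689 and leaves the other two (a) counts out of 990 unchanged. Omitted hormone-free intervals are not modelled; they would lower both counts.

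**The case against.** The SAP choice is explicit and labelled, and Protocol 12 leaves detailed methods to the SAP. Counting only days with a recorded pill is the cautious direction for a safety-exposure row. Much of the missing information is planned elsewhere: SAP 9.3.1 also summarises total exposure and the number of women by cycles started, and SAP 9.1 gives completers. No decision rests on the row. The modelled counts run from 26 to 753 of 990 on assumed rates alone, and they ignore the diary review at visits, which may reduce blanks. Calendar span has its own fault: 12 packs with 28 gap days in total also reach 364 days, on only 336 pill-days.

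Most of this stands as a limit on importance. The row is descriptive, the size is unknown, and calendar span does count off-drug days. It does not rescue the rule. A measure that passes a 2-day gap between packs and fails one skipped placebo tablet is not simply cautious; at this threshold it mainly tests unbroken diary entry within packs. Total exposure is planned only as descriptive statistics, with no 52-week count. Under SAP 5.1 the last cycle ends at the last dose, so the row for at least 13 cycles can include women who only began Cycle 13. The SAP itself treats pill-free time between first and last dose as on-treatment (5.3) and uses total exposure for adverse event rates (5.8, 9.6.1).

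**Conclusion.** The concern holds. SAP 5.8 and 9.3.1 depart from Protocol 12.5.2 without explanation. Because 13 × 28 = 52 × 7, on the normal schedule one within-cycle missed or blank day removes a 13-cycle completer from the 52-week count. The arithmetic needs no assumption; the number of women affected does. Over the assumed daily rates, the share of completers lost from the row runs from 24% (0.1%, rates varying between women) to 97% (1%, one common rate), against 0.1% to 1% on total exposure. The 26-week count is not materially affected for completers. The Pearl Index, adverse event rates, completer counts and counts by number of cycles are unaffected. It should be fixed, but it concerns one descriptive row.

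**What to change.** In SAP 5.8 and 9.3.1, base the 26- and 52-week counts on total exposure (last dose date − first dose date + 1), as in Protocol 12.5.2. Show beside them the number of women who completed 13 cycles, because total exposure also fails a woman who misses only the last tablet (363 days) or omits one hormone-free interval (360 days). Keep the actual-exposure counts as a labelled supplementary line, so that interruptions which total exposure counts as exposure remain visible; that is the small downside of the change. Record the change in the amendment log. The cost is SAP wording and one derived flag, with no new data.
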